# **Study Title**

Intravenous hydrogen nanobubbles effect on cardiac physiology and quality of life: a single blind, dose-response study

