# **Study Design**

This study is a randomized, single-blind, dose-response clinical trial conducted to assess the effects of intravenous hydrogen nanobubbles (HNBs) on multiple health outcomes, including cardiac physiology, quality of life, and blood biomarkers. Participants were randomly assigned to one of six groups and received either HNB infusion or normal saline (control) over a 5-week period (10 sessions total, twice per week). The intervention doses were 0 mL (control), 5 mL, 10 mL, 15 mL, 20 mL, and 25 mL of HNB diluted in 500 mL of normal saline.

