### **Outcome Measures**

Primary outcomes were assessed at baseline (week 0) and post-intervention (week 5):

- 1. Cardiovascular physiology: systolic and diastolic blood pressure (mmHg), heart rate (bpm), LVMI (g/m²), RWT (unitless), TAPSE (cm), and FMD (% change).
- 2. Quality of Life: measured using the SF-36 questionnaire.
- 3. Blood profile: inflammatory markers, lipid profile, liver function tests, and hematologic indices.

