## **Statistical Analysis Plan**

Statistical analyses were conducted to evaluate time-related changes and dose-dependent effects.

- Repeated Measures ANOVA was used to assess within-subject changes (pre- vs post-treatment) and interaction effects between dose and time.
- The Bayesian paired t-test was applied to complement the ANOVA results, providing Bayes Factors ( $BF_{10}$ ) that quantify the strength of evidence supporting the treatment effect.
- A p-value < 0.05 was considered statistically significant. BF10 values > 3 indicated moderate evidence, > 10 strong evidence, and > 100 very strong evidence for the alternative hypothesis.
- Data analysis was performed using appropriate statistical software, and each outcome was treated independently without aggregation into composite indices.

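### The plan for a dose-response trial does not state how dose is coded and names no trend or slope; if dose is a six-level factor, its one dose test ignores dose order

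*Combined protocol and SAP*

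**What the plan says.** The Study Title calls the trial "a single blind, dose-response study". Under Study Design, "Participants were randomly assigned to one of six groups", and "The intervention doses were 0 mL (control), 5 mL, 10 mL, 15 mL, 20 mL, and 25 mL of HNB". The Outcome Measures section has two assessments, at week 0 and week 5.

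The Statistical Analysis Plan opens with its aim: "Statistical analyses were conducted to evaluate time-related changes and dose-dependent effects". Two methods follow. The repeated measures ANOVA covers within-subject change and "interaction effects between dose and time". Then, "The Bayesian paired t-test was applied to complement the ANOVA results"; this second method is described without reference to dose. The significance level is 0.05.

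The plan does not say whether dose enters the ANOVA as a six-level factor or as a number. It names no trend contrast, slope, dose-response model or dose-versus-control comparison.

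**The concern.** Six equally spaced dose levels are a good basis for estimating how response changes with dose. The plan does not say that it will use that spacing, or even the order of the doses.

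If dose is a factor, two errors of interpretation are possible. A significant interaction can come from an irregular pattern with no trend and then be reported as a dose-response. A real, roughly linear gradient can be missed because the test spreads its power over five degrees of freedom. If dose is a number, the interaction already tests a slope, but readers are not told so and are promised no estimate of it. Under either coding, the plan does not commit to a slope with which a reader could judge the question in the title.

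**Working it through.** **Inputs.** From the documents: six arms (0, 5, 10, 15, 20, 25 mL), two time points, alpha 0.05. The documents give no sample size, SD, effect size or power, so there is no figure of the plan's own to reproduce. Assumed for illustration: 10 or 20 per arm, equal arms, equal SD of change, two-sided testing. Effects are in SDs of the week 0 to week 5 change.

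**Degrees of freedom.** As a factor: (6 − 1) × (2 − 1) = 5. As a number: 1.

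**Does the 5-df test use dose order?** With two time points, the interaction equals a one-way ANOVA on change. In one simulated data set (10 per arm), the interaction F was 2.816, the one-way F on change was 2.816, and F after shuffling the dose labels was 2.816. The slope t moved from 0.87 to −1.40. So the factor test is blind to order and the slope is not.

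**Power formulas.** Both tests use error df 6n − 6 (54 or 114) and the noncentral F distribution.
- 5-df test: ncp = n × Σ(mᵢ − m̄)².
- Linear contrast: ncp = n × (Σcᵢmᵢ)² / Σcᵢ², with c = −5, −3, −1, 1, 3, 5 and Σc² = 70.

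**Exactly linear truth.** Let D be the difference in mean change between 25 mL and control. Then Σ(mᵢ − m̄)² = 2 × (0.25 + 0.09 + 0.01) × D² = 0.7D², and both tests have the same ncp.

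| Per arm | D | ncp | 1-df trend | 5-df test |
|---|---|---|---|---|
| 10 | 1.078 | 8.138 | 80.0% | 52.4% |
| 20 | 0.755 | 7.983 | 80.0% | 54.0% |

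The gap depends on shape and size. At D = 0.8 (5-df against trend): linear with 20 per arm, 60% against 84%; linear with 30 per arm, 81% against 95%; a saturating curve (half-maximal effect at 5 mL) with 20 per arm, 60% against 75%.

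**A pattern with no trend.** For mean changes 0, 1, 0, 0, 1, 0 SD, the contrast is (−3)(1) + (3)(1) = 0, so it rejects 5% of the time. The 5-df test rejects 77.1% (10 per arm) or 98.6% (20 per arm). At 0.5 SD it rejects 22.4% or 45.7%.

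**Where the linear contrast is weak.** Effects are scaled so that the 5-df test has 80% power (ncp 14.196 and 13.462):

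| Shape | Linear contrast, 10 / 20 per arm |
|---|---|
| Step at first dose, or top dose only | 67.8% / 66.3% |
| Quadratic umbrella peaking at 15 mL | 55.2% / 53.8% |
| Equal-step umbrella 0, 1, 2, 3, 2, 1 | 39.7% / 38.6% |
| Symmetric umbrella 0, 1, 2, 2, 1, 0 | 5% (−3 − 2 + 2 + 3 = 0) |

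**Price of two tests.** If either test at 0.05 could count as a dose effect, the simulated false-positive rate per outcome is 8.56% / 8.59%, against 5% for one test.

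**The case against.** The strongest reply is that nothing in the plan is invalid. Arms are randomised and are described as differing only in dose, so a global test among them does address whether response depends on dose. The documents specify no shape. This stands. A reader might infer that the interaction cannot speak to dose effects at all, or that only a linear trend may support any dose-response statement. The documents support neither. A threshold or umbrella is also a form of dose-response, and a linear contrast can miss it almost entirely.

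Second, the order-blindness depends on coding that the SAP does not state. A reader might infer that dose was certainly a factor. That is the usual form of a repeated measures ANOVA, but the text does not settle it. If dose was numeric, only the statement of coding and the slope report are missing.

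Third, an exactly linear truth is the best case for the linear contrast, and the trendless pattern was built to make the contrast zero. Both are illustrations and do not measure a loss in this trial.

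Fourth, the documents are written in the past tense, so a trend analysis may come too late to be prespecified, and it would add a test to each of many outcomes. This limits the benefit, but a slope with its interval would still inform readers.

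**Conclusion.** The concern holds as an inexpensive improvement to the analysis and its reporting. It is certain that the coding of dose is unstated and that no trend or slope is named, in a plan whose title and aim concern dose. It is conditional on factor coding that the one dose test ignores order. That test then remains valid for differences among arms, but its p-value alone does not show an ordered dose-response.

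The size is illustrative: about 26 to 28 percentage points of power (80% less 54.0% or 52.4%) for an exactly linear gradient at 10 to 20 per arm, equal SDs and two-sided 0.05. It is smaller for saturating curves and larger samples, and it reverses for step and umbrella shapes. This is why the trend should be added to the global test and should not replace it.

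**What to change.** State in the Statistical Analysis Plan whether dose is a six-level factor or a number.

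- **If a factor:** for each outcome, add a linear contrast on week 0 to week 5 change with coefficients −5, −3, −1, 1, 3, 5, or a regression of change on dose. Report the slope with its 95% confidence interval. The slope per mL is the contrast of arm means divided by 175 (2.5 × 70).
- **If already a number:** say so and report that slope with its interval. No further trend test is needed.
- **Show the shape:** give each arm's mean change with its interval, because a significant slope can also come from a step.
- **State the role of each test:** the trend carries any claim of an increasing or decreasing dose-response. The 5-df interaction is the global test of whether response differs among doses. Threshold or umbrella patterns are described from the global test and the arm means. A multiple-contrast test over several candidate shapes is an option.
- **Timing:** if the data have already been examined, label the trend analysis post hoc.

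The cost is a few lines of text and one contrast per outcome, with no new data. The downside is one more test per outcome: unless the roles are fixed, the false-positive rate rises to about 8.6% for each outcome, and this adds to the multiplicity across the plan's many outcomes.

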### **Intervention Details**

Group A (Control): 500 mL normal saline

Group B: 5 mL HNB in 500 mL NS Group C: 10 mL HNB in 500 mL NS Group D: 15 mL HNB in 500 mL NS Group E: 20 mL HNB in 500 mL NS Group F: 25 mL HNB in 500 mL NS

Each group received 10 intravenous sessions over 5 weeks (2 sessions/week).

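### The Bayes factor offered as evidence of the treatment effect comes from a paired pre-post test with no HNB-versus-saline contrast

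*Combined protocol and SAP*

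**What the plan says.** The Study Design section describes a randomised trial "conducted to assess the effects of intravenous hydrogen nanobubbles (HNBs) on multiple health outcomes", in which participants in six groups "received either HNB infusion or normal saline (control) over a 5-week period". Intervention Details identifies the comparator: "Group A (Control): 500 mL normal saline". Under Outcome Measures, the primary outcomes are measured twice, at week 0 and at week 5.

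The Statistical Analysis Plan opens with two aims: "Statistical analyses were conducted to evaluate time-related changes and dose-dependent effects". It then specifies two analyses.

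- A repeated measures ANOVA, covering within-subject change and "interaction effects between dose and time".
- A Bayesian paired t-test: "The Bayesian paired t-test was applied to complement the ANOVA results". Its Bayes factors are said to be ones "that quantify the strength of evidence supporting the treatment effect".

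BF10 is graded moderate above 3, strong above 10 and very strong above 100, in favour of an alternative hypothesis that is not defined. The plan does not say which arms enter the paired test, what prior is used, or how the grades relate to the interaction.

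**The concern.** In a randomised trial with a saline control, the effect of HNB is the difference in change between HNB and saline. A paired t-test looks only at change within people. It can serve the first of the plan's two aims, change over time, but the plan presents its Bayes factor as evidence for the treatment effect.

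The distinction matters for outcomes that can move in every arm. SF-36 scores, blood pressure and heart rate could shift through placebo response, habituation to measurement, or ten infusions of 500 mL whatever they contain. If so, a report that follows the plan could call the shared shift moderate or strong evidence of a treatment effect while the randomised comparison shows nothing. The saline arm and the blinding exist to separate these two things, and the paired test does not use them as a comparison.

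**Working it through.** **No figure to reproduce.** The documents give no sample size, effect size, SD or power. The point rests on what each test estimates; the percentages only illustrate it.

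**1. What each test estimates.** With two visits, each participant contributes one change score, week 5 minus week 0. Write its mean in arm j as δ + τ_j, where δ is change shared by all arms and τ_j is the effect of HNB dose j over saline (τ = 0 for Group A).

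- Paired t-test, one arm: the null is δ + τ_j = 0.
- Paired t-test, arms pooled: the null is δ + (average τ over those arms) = 0.
- Dose-by-time interaction, which with two visits is a one-way ANOVA on change scores: the null is that all τ_j are equal. δ cancels.

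So if every τ_j is zero but δ is not, the paired test's alternative is true and its BF10 grows with sample size. This holds for single arms, pooled HNB arms or all participants.

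**2. Assumptions for the illustration (none is in the documents).** No HNB effect; the same drift d in all six arms, in SDs of the change score; normal change scores; a Cauchy prior of scale 0.707; 10 or 20 participants per arm.

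**3. Cut-offs.** Solving the JZS paired Bayes factor for |t|:

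| n in the test | t for BF10 = 3 | t for BF10 = 10 |
|---|---|---|
| 10 | 2.684 | 3.625 |
| 20 | 2.561 | 3.219 |
| 50 | 2.578 | 3.095 |
| 100 | 2.648 | 3.113 |

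**4. Exceedance.** The probability that |t| passes the cut-off comes from a noncentral t with n − 1 df and noncentrality d√n. For n = 50 and d = 0.3 the noncentrality is 0.3 × √50 = 2.12, giving 33.4%.

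| Paired test with no HNB effect | d = 0 | 0.2 | 0.3 | 0.5 |
|---|---|---|---|---|
| One HNB arm, n = 10, BF10 > 3 | 2.5% | 4.8% | 7.9% | 19.2% |
| One HNB arm, n = 20, BF10 > 3 | 1.9% | 6.6% | 13.7% | 39.5% |
| Five HNB arms pooled, n = 50, BF10 > 3 | 1.3% | 13.3% | 33.4% | 82.6% |
| Five HNB arms pooled, n = 50, BF10 > 10 | 0.3% | 5.6% | 18.0% | 66.9% |
| Five HNB arms pooled, n = 100, BF10 > 3 | 0.9% | 26.4% | 63.8% | 99.0% |

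If each HNB arm is tested separately, the chance that at least one passes BF10 > 3 is 1 − (1 − p)^5. At n = 10 this is 11.9%, 21.8%, about 34% and 65.5% across the four drifts. The 11.9% is multiplicity alone; only the excess over it is due to drift.

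**5. Between-arm comparators under the same conditions.** None depends on d.

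- The interaction F test (5 and 6(n − 1) df) is significant in about 5% of simulated trials at every drift.
- A two-sample BF10 for one HNB arm against saline exceeds 3 at t = 2.516 (n = 10) and t = 2.441 (n = 20), with null probabilities 2.2% and 1.9%.
- A BF10 on the six-level dose-by-time term (prior scale 0.5) exceeds 3 at F = 2.972 (n = 10) and F = 3.027 (n = 20), with null probabilities 1.9% and 1.3%.

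**6. Disagreement between the two analyses.** In simulated six-arm trials with 10 per arm, a pooled paired BF10 above 3 occurs together with a non-significant interaction in 1.2%, 12.5%, 31.6% and about 79% of trials at drifts 0, 0.2, 0.3 and 0.5. The plan has no rule for this case.

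**The case against.** The plan contains a correct randomised comparison. The dose-by-time interaction tests differences in change between arms, the Bayesian test is described only as a complement, and a paired test is a proper tool for the stated aim of describing change over time. No success rule is attached to BF10 > 3. For a paired test the natural alternative is non-zero pre-post change, and the authors may have meant treatment effect in just that sense. If the saline arm was also tested, readers would see the shared drift there. The larger percentages need a drift of 0.5 SD in every arm, or pooling, or counting any of five arms; one arm at 0.2 SD gives only 4.8 to 6.6%.

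Much of this stands. Including a paired test is not an error, no between-arm test is missing, and the size of any drift is unknown. What does not stand is that these points settle the matter. Calling the test a complement does not say which result carries the treatment claim, and the p < 0.05 criterion is not assigned to the interaction either. Comparing one arm's Bayes factor informally with saline's is not a test of the difference, and no such comparison is planned. If pre-post change was meant, the sentence should say so.

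**Conclusion.** The concern holds. The paired Bayes factor measures evidence of change over time and cannot, by itself, grade evidence for HNB over saline. That conclusion follows from the design and needs no assumed number.

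How much it matters depends on shared drift, which the documents do not quantify. With zero drift this mechanism adds nothing. With drift of 0.2 to 0.5 SD under the assumptions above, a BF10 above 3 without any HNB effect occurs in about 5 to 39% of trials for one arm, and in about 13 to 99% for the five HNB arms pooled. The between-arm Bayes factors stay at about 1 to 2%. Drift is plausible for SF-36, blood pressure and heart rate; none is argued here for LVMI or RWT. This should be fixed. It affects what may be claimed from the Bayes factors and leaves the validity of the interaction test untouched.

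**What to change.** **Minimum.** In the Statistical Analysis Plan, and in any report based on it:

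- state that claims of a treatment effect rest on the dose-by-time term;
- state that the paired Bayes factor and the ANOVA time effect describe within-arm change only;
- name the arms entered in each paired t-test.

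This is a change of wording only.

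**Optional, only if a Bayes factor is to grade the treatment effect.** For each outcome, compute BF10 for the model with the dose-by-time term against the model without it. State the prior and whether dose is coded as six levels or as linear, and apply the 3/10/100 grades to that quantity. This is a re-analysis of existing data; no new data are needed. The resulting Bayes factors will usually be less favourable, because change shared with saline no longer counts.

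### At least 12 outcomes are labelled primary and each is tested at p<0.05, with no multiplicity adjustment, testing order, lead outcome or rule for a positive trial stated

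*Combined protocol and SAP*

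**What the plan says.** The Outcome Measures section introduces its whole list with "Primary outcomes were assessed at baseline (week 0) and post-intervention (week 5") and has no secondary tier. The first group contains "systolic and diastolic blood pressure (mmHg), heart rate (bpm), LVMI", followed by RWT, TAPSE and FMD, which makes seven measures. The second is quality of life, "measured using the SF-36 questionnaire", without saying which scores. The third is a blood profile in four classes (inflammation, lipids, liver function, haematology), with no analytes named.

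The Statistical Analysis Plan sets out to "evaluate time-related changes and dose-dependent effects". Repeated measures ANOVA supplies the pre-to-post change and the "interaction effects between dose and time". The error rule is one sentence: "A p-value < 0.05 was considered statistically significant". The section adds that "each outcome was treated independently without aggregation into composite indices". On the Bayesian side, "The Bayesian paired t-test was applied to complement the ANOVA results", with fixed evidence thresholds and no correction across outcomes.

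No section states a multiplicity adjustment, a testing order, a lead outcome or how many significant results would make the trial positive. No redaction is visible that could account for this.

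**The concern.** A 5% threshold describes the error of a claim only when the claim rests on one test. Here at least 12 outcomes share primary status and none leads. A reader who sees one significant primary result cannot tell a treatment effect from one chance hit among many tests. The number of tests is not fixed either, because the SF-36 and each blood class can produce several scores or analytes. This touches every efficacy statement the trial could make.

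**Working it through.** The plan gives no sample size, power or overall error rate, so there is no figure of its own to reproduce.

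**Inputs from the documents.** Threshold 0.05 per test (Statistical Analysis Plan). Six groups (Study Design), so the interaction has 5 numerator df if dose is categorical. Two assessment times (Outcome Measures), so the dose-by-time test is equivalent to a one-way F test on change scores. Outcome count: 7 + 1 + 4 = 12, a minimum that counts the SF-36 once and each blood class once.

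**Assumptions, because the documents give no figures.** Equal pairwise correlation r from 0 to 0.9; 10 participants per arm; 30 outcomes as an illustration of scales and analytes tested one by one. Under the null, HNB affects no outcome. One dose-by-time test is counted per outcome.

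**Independent outcomes.** Chance of at least one p<0.05 is 1 − 0.95^K:
- K = 7: 1 − 0.95^7 = 0.302
- K = 12: 1 − 0.95^12 = 0.460
- K = 30: 1 − 0.95^30 = 0.785

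**Correlated outcomes.** Simulated change scores, 200,000 trials, chance of at least one p<0.05:

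| Test and number of outcomes | r=0 | 0.3 | 0.5 | 0.7 | 0.9 |
|---|---|---|---|---|---|
| 5-df F, K=7 (cardiovascular only) | 30% | 28% | 24% | 19% | 12% |
| 5-df F, K=12 | 46% | 41% | 34% | 26% | 15% |
| 5-df F, K=30 | 79% | 68% | 54% | 38% | 19% |
| Linear dose, 1 df, K=12 | 46% | 40% | 32% | 24% | 14% |
| 5-df F, K=12, Holm | 4.9% | 4.7% | 4.2% | 3.3% | 1.8% |

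Arm size hardly matters. At r = 0.5 and K = 12 the 5-df rate is 34.7% with 5 per arm and 33.7% with 20.

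**Separate claims.** Expected false positives are K × 0.05 whatever the correlation: 7 × 0.05 = 0.35; 12 × 0.05 = 0.6; 30 × 0.05 = 1.5.

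**Power cost of adjustment.** The first Holm step is 0.05/12 = 0.0042, or 0.05/30 = 0.0017. Power is the upper tail of a noncentral F beyond the critical value, with the effect set to give 80% at 0.05 and 10 per arm:

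| Effect has 80% power on | Tested by | at 0.05 | at 0.05/12 | at 0.05/30 |
|---|---|---|---|---|
| 5-df test | 5-df test | 80% | 45% | 33% |
| 1-df linear trend | 1-df trend | 80% | 45% | 34% |
| 1-df linear trend | 5-df test | 52% | 18% | 12% |

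The last row shows what dose coding does. If the response is linear in dose, the 5-df test has already lost power before any adjustment. Over 5 to 30 per arm, the first row runs 41–47% at 0.05/12 and 28–36% at 0.05/30.

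No rate is given for the time effect. It can be real in every arm, control included, when HNB does nothing.

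**The case against.** The strongest objection is that 46% depends on a decision rule the documents do not contain. A reader might infer that the trial has a 46% type I error; the text does not support that. Treating outcomes one at a time fits separate claims at least as well, and then each test is valid at 5%. This stands, so the percentages are conditional. What remains is that no other rule is given, and separate claims still carry 0.6 expected false positives per 12 tests.

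A reader might also infer that the plan declares its p-values unadjusted. It does not. Its remark on independence is explained by the absence of composites. Non-adjustment is inferred from silence, and the exact statement is that no adjustment is stated.

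The equal correlations have no basis in the documents, and 0.9 across blood pressure, echocardiography, SF-36 and liver tests is hard to credit. The range therefore shows sensitivity and is not an estimate. Nor is the inflation large everywhere: seven outcomes at r = 0.9 give 12%, which is 12/5 = 2.4 times nominal.

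Two objections to the remedy also stand. Imposing a 5-df test on a dose-response study would go beyond multiplicity and carry the power loss shown above. Requiring adjusted significance for liver and haematologic results could hide adverse changes, and the documents do not say whether those tests serve efficacy or safety. The fix allows for both.

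The Bayes factors do not remove the problem: their stated role is complementary, and they too are read outcome by outcome.

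**Conclusion.** The concern holds in a limited form. The plan has at least 12 primary outcomes and one 5% threshold, and it defines neither the family of tests nor what would count as a positive trial. If any one significant dose-by-time result is taken as evidence that HNB works, the false-positive chance for an inert product is about 46% under independence and about 34% and 15% at assumed correlations of 0.5 and 0.9. For the seven cardiovascular measures alone it is about 30%, 24% and 12%. These figures rest on the assumed reading, equal correlations and one test per outcome; arm size has little effect. They rise if SF-36 scores and analytes are tested separately. The documents do not support saying that individual tests are invalid or that any particular result is false. The gap should be closed before any primary result is presented as a confirmed benefit.

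**What to change.** 1. List the SF-36 scores and blood analytes that count as primary, from trial records and not from results. If no such list exists, include every score and analyte measured at both week 0 and week 5.
2. Use one dose-by-time p-value per outcome as the basis for a treatment claim. State whether dose was planned as six groups (5 df) or as a linear trend (1 df), and do not choose between them from results. Holm works with either; the 5-df test ignores dose order.
3. Report Holm-adjusted p-values across the listed primary outcomes beside the unadjusted ones. Base any claim of confirmed HNB benefit on the adjusted values. Present time effects, Bayes factors and unadjusted results as supportive.
4. Do not require the adjusted threshold for reporting adverse changes in liver, haematologic or other measures.
5. The text is in the past tense. If data have been seen, keep every primary-labelled outcome in the family, or label any demotion post hoc. A single lead outcome or fixed order would also control the error, but only if documented before results were known.

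The work is SAP wording, an outcome list from trial records, and a recalculation of p-values. The price is lower power per outcome, as tabulated above, and it grows with the number of analytes counted. Later Holm steps are less strict than the first.
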